36.	Partial Waiver of Consent for Screening/Recruitment	25
37.	Partial Waiver of HIPAA Authorization for Screening/Recruitment.....	26
38.	Waiver of Documentation of Consent	26
39.	Alteration of Consent.....	27
40.	Full Waiver of Consent/Parental Permission.....	28
41.	Full Waiver of Consent/Parental Permission (Public Benefit or Service Programs)	
	29	
42.	Full Waiver of HIPAA Authorization (Checklist).....	29
43.	Other Waiver Types (Checklist).....	30

44.	Vulnerable Populations (Checklist).....	30
45.	Medical Devices (Checklist).....	36
46.	Export Control (Checklist)	37
47.	Data Transfer/Sharing (Checklist).....	37
48.	Specimen Transfer/Sharing (Checklist).....	38

1. Objectives

1.1. Describe the purpose, specific aims, or objectives.

Our long-term goal is to develop a mindfulness-based intervention (MBI) program that significantly decreases stress/burnout and increases belongingness and connectedness among nurse faculty and staff. The overall objective of this pilot project, which is the next step in toward achievement of our long-term goal, is to examine the feasibility and preliminary efficacy of MBIs as an intervention for University of New Mexico (UNM) Health Sciences Center (HSC) nurse faculty and staff. Our central hypothesis is that this MBI intervention will improve the psychosocial outcomes (sense of belonging) and physiological outcomes (HRV) among HSC nurse faculty and staff. To test our central hypothesis and attain the overall objective, we will pursue the following specific aims:

Aim 1. To evaluate the feasibility and acceptability of MBIs (meditation or yoga) for HSC nurse faculty and staff. Acceptability will be assessed qualitatively from analyses of interviews with participants. Feasibility will be assessed as rates of recruitment, retention, and adherence to the MBI (% training sessions attended).

Aim 2. To evaluate the preliminary effect of MBI (meditation; yoga) in HSC nurse faculty and staff on: psycho-social outcomes (burnout; sense of belonging, stress, anxiety) and physiological outcomes (HRV evaluated by wearable electronics). We hypothesize that: a) psycho-social outcomes will improve post-intervention and b) physiologic measures (HRV) will improve post intervention compared to preintervention.

1.2. State the hypotheses to be tested.

Our central hypothesis is that this MBI intervention will improve the psychosocial outcomes (sense of belonging) and physiological outcomes (HRV) among HSC nurse faculty and staff.

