5.3. Provide sample size justification

The planned overall sample size of 30 is consistent with recommendations for pilot studies seeking to build evidence in the context of medium effect size differences between two groups.¹⁸

6. Study Timelines

6.1. Describe:

- *The duration of an individual subject's participation in the research*
- *The duration anticipated to enroll all subjects*
- *The expected duration for the investigators to complete the study (complete analysis)*

Participants will be enrolled until the allotted 30 participants for the first 6 weeks of the study is reached. The study is comprised of a pre-intervention assessment, followed by 6 weeks of meditation/yoga attendance (twice/week). Upon completion of the 6-week intervention, participants will complete a post intervention assessment (See Table 1.).

Table 1. Study Timeline	Months									
	1	2	3	4	5	6	7	8	9	10
Prepare research and data management tools.		→								
Session 1										
Recruitment		→								
Intervention		→	→							
Data Collection		→	→							
Preliminary Data Analyses				→						
Session 2										
Intervention				→						
Data Collection				→						
Analyses					→					
Prepare R01 proposal										→
Dissemination										→

7. Study Endpoints: Primary endpoint(s) are typically efficacy measures that address the main research question. Secondary endpoints are generally not sufficient to influence decision-making alone, but may support the claim of efficacy by demonstrating additional effects or by supporting a causal mechanism.

7.1. *Describe the primary and secondary study endpoints.*

Primary outcomes of interest of this study include the feasibility and acceptability of mindfulness-based interventions (MBI) (Aim 1). We will also examine the preliminary effect of these interventions on psychosocial outcomes (primary: sense of belonging; secondary: burnout, stress) and physiologic outcomes (HRV) (Aim 2).

7.2. *Describe any primary or secondary safety endpoints.*

This is a minimal risk study.

7.3. *Describe any exploratory endpoints.*

N/A There are no anticipated exploratory endpoints.

8. Research Setting

8.1. *Describe the sites or locations where your research team will conduct the research.*

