Potential participants will be recruited from the UNM HSC. The UNM HSC currently employs 71 faculty and 71 staff in the CON, plus nurse faculty and staff in other HSC programs. Study personnel will conduct all screenings in the private clinical research rooms housed within the CON Research Laboratory suite.

8.2. *Identify where your research team will identify and recruit potential subjects.*

Potential participants will be identified and recruited from the UNM CON.

8.3. *Identify where research procedures will be performed including any laboratory analytics*

Informed consent and research visit interviews will occur in private clinical research rooms housed within the UNM CON Research Laboratory suite. Questionnaires will be administered via secure REDCap survey. Garmin devices will be distributed and/or collected after completion of questionnaires. Meditation and yoga sessions will occur in the Collaborative Research Space housed within the CON Research Laboratory suite.

8.4. *Describe the composition and involvement of any community advisory board*

N/A, this study does not involve a community advisory board.

8.5. *For research conducted outside of UNM HSC and its affiliates describe:*

- *Site-specific regulations or customs affecting the research*
- *Local scientific and ethical review structure/requirements (Note: include any approvals (IRB, facility, or other) with your submission)*

N/A, this is a single site study.

9. Resources Available

9.1. Describe the qualifications of the PI and study staff (e.g., training, experience, oversight) as required to perform the research. When applicable describe their knowledge of the local study sites, culture, and society.

The PI, [name], has been a registered nurse for the past 37 years. In addition, [name] is an Associate Professor in the UNM CON and has been a faculty member of the UNM CON since 2013. She has extensive experience in the evaluation of stress and collection of both biological and behavioral research data. Additionally, [name] has successfully conducted research employing mobile ecological momentary assessment.^{19,20} [name] is also a Registered Yoga Teacher (RYT) 200 and will lead the yoga intervention.

[name] (Co-Investigator) has been a registered nurse for the past 35 years, a professor for 14 years and at the UNM CON for 4 years. She is part of a fellowship in contemplative medicine. In addition, she has 15 years of mindfulness practice and is an ordained Soto Zen Priest.

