Mobile Ecological Momentary Assessment (mEMA): Ambulatory assessment via mEMA allows for real time sampling within the individual's natural environment at multiple time points throughout the day. The Ilumivu mEMA (<https://ilumivu.com>) platform (iOS and Android compatible) is HIPPA compliant. The platform does not require any personally identifying information from participants. The platform automatically generates a unique identifying code. A research team member will provide this code to the participant to enter into their mobile app. Data are sent from the sensor to the mEMA app on the phone directly via Bluetooth. Data are then uploaded to Ilumivu's servers when the individual is within range of WiFi. Surveys are timestamped upon completion. All data are encrypted on transmission and stored securely. Datasets are only available to authorized research team members.

Following completion of baseline surveys, participants will be instructed to install the Ilumivu mEMA application on their smart-phone. The participants will be trained on how to access and respond to mEMA surveys. Participants will be asked to complete three mEMA assessments per day (morning, afternoon, and evening). An alert will be programmed to be sent at pre-determined times to remind the participant to complete the survey. All questions will be multiple choice (see MAAS-State below).

mEMA outcome: *State mindfulness* will be measured using the 5-item MAAS-State scale completed on the IlumiIvu mEMA app. The MAAS-State was designed to assess the expression of the core characteristic of mindfulness in real-time.²³

Physiologic Outcome Measures. Ambulatory assessment of physiological processes within the context of an individual's daily life will occur through use of a wearable wrist electronic sensor. This platform provides direct, real-time data which is sent from the wearable sensor to the mEMA app, by Bluetooth.

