Physiologic measures: inter-beat-interval will be collected via a Garmin Vivosmart5® device. This device has been shown to produce reliable heart rate data with the mean absolute percentage error below the designated acceptable 10% threshold.³¹ Each participant will receive training for use of the sensor and written instructions will be provided for future reference. Participants will wear the device on their non-dominant hand in their daily environment every day for six weeks. Daily reminders to wear the device and to check the battery level will be delivered via the mEMA to increase compliance with the protocol.

HRV outcome measures: Garmin Vivosmart5® uses optical technology in which a series of lights emitted by photoplethysmography (PPG) sensors against the skin illuminate capillaries to detect changes in blood volume and providing heart rate data in real time.³¹ Raw data is collected from the device and sent to the phone via Bluetooth. Using the pulse to pulse (P-P) interval, inter-beat-interval (IBI) is derived via Ilumivu software. HR epochs of five-minute intervals immediately preceding and corresponding to each mEMA survey will be selected for analysis. Time and frequency domain analysis will be performed by Ilumivu using proprietary software. **Time Domain measures:** Time domain measures are based on the time difference between easily detectable QRS complexes.

Using PPG technology, these measures are derived from the P-P interval (distance in milliseconds between each P). Simple time domain measures (standard deviation of P-P interval, mean HR) will be calculated. Frequency domain measures estimate frequency spectrum. The general bands are low frequency (LF; 0.04–0.15 Hz) and high frequency (HF; 0.15–0.40 Hz). Low frequency measures, high frequency measures, and LF/HF ratio of HRV will be computed.³²

Long-term HRV, 24 hour time windows, will be determined by dividing the 24 hour time period into consecutive 5 minute epochs and averaging the individual values of the HRV metrics to obtain the mean of the value within the 24 hour time window.^{32,33} Five-minute heart rate epochs immediately following completion of each mEMA survey will also be selected for analysis.^{20,34} Between subject variability, in which relatively stable variation is compared between individuals, and within-subject (WS) variability, in which variation within the same individual across time will be examined.

12.4. Indicate what study activities happen when and where.

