Description of Intervention Delivery

These guidelines detail the procedures used to conduct Mindful Meditation or Yoga sessions.

We will employ a quasi-experimental design to assess feasibility, acceptability, and preliminary efficacy of MBIs (meditation; yoga) to increase a sense of belonging and connectedness in academic nursing faculty and staff. We will assign 15 individuals to each condition. Across both conditions, all participants will participate in one baseline assessment/training session, 6 weeks of MBIs (participants will be required to attend 2 sessions per week), and a post-intervention assessment session. Following screening for inclusion/exclusion criteria, eligible participants will complete the **BEING Mindful** Exercise participation screening. Eligible participants will provide informed consent.

Assignment of Participants:

After informed consent is obtained, research staff will allocate individuals to meditation vs yoga on a 1:1 basis. If an individual is unable to participate in the yoga arm, they will be assigned to meditation and the next two participants will be assigned to yoga.

Retention:

To promote retention, we will reach out to participants with frequent reminders via text messages and emails.

Baseline Assessment session: During the baseline assessment session, participant characteristics will be collected. Baseline self-report questionnaires will be completed: 1) Sense of Belonging Scale (SBS); 2) Mindfulness Attention Awareness Scale (MASS) 15-item; 3) Generalized Anxiety Disorder-7 (GAD-7); 4) NIH toolbox measure of perceived stress.

Intervention Delivery:

The meditation and yoga interventions are 6-week protocols. We will offer meditation sessions 4 times per week and yoga sessions 4 times per week. We will require participants to attend two sessions per week. Attendance will be tracked via the Ilumivu platform. Participants will be requested to log attendance at each session via the app.

The meditation intervention will be led by [name] and [name]. Meditation is a practice of mental exercises designed to increase focus and cultivate a desire to relieve suffering in self and other.^{35,36} The practice dates back millennia to Buddhist and Hindu sages, but more recent work focuses on stress.³⁷ More recently, the term mindfulness has been used which means awareness, attention, and remembering.³⁷ Many religious traditions have a form of meditation based practice. This study will focus

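### The plan neither secures a pre-intervention HRV window nor tests pre-to-post HRV change, so Aim 2(b) is not tested as written

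*Combined protocol and SAP*

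**What the plan says.** **Hypothesis.** Section 1.1, Aim 2(b), predicts that "physiologic measures (HRV) will improve post intervention compared to preintervention". HRV is also the physiological half of the central hypothesis.

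**Recording period.** Section 12.3 states: "Participants will wear the device on their non-dominant hand in their daily environment every day for six weeks". Section 12.5 states: "The meditation and yoga interventions are 6-week protocols". Section 6.1 places a pre-intervention assessment ahead of the six weeks of sessions but gives no interval between them.

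**Set-up and return.** Section 8.3 says: "Garmin devices will be distributed and/or collected after completion of questionnaires". Section 12.3 adds: "Following completion of baseline surveys, participants will be instructed to install the Ilumivu mEMA application on their smart-phone". The sensor data pass through that app. The baseline and post-intervention visit lists in section 12.5 contain questionnaires (plus an interview at the end) but no HRV recording.

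**HRV summaries.** Section 12.3 defines five-minute epochs around each app survey, and 24-hour averages of five-minute epochs. It does not say which days count as before or after the intervention. It also says that "variation within the same individual across time will be examined", without naming a contrast.

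**Analysis.** Section 13.1 compares long-term HRV between the two arms by t-test. Its general text for continuous outcomes compares changes from baseline between arms with non-parametric tests. It also gives Cohen's d within and between arms, explicitly as a description.

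**The concern.** The hypothesis concerns change within a person, but the HRV test concerns a difference between two active arms. If meditation and yoga both raise HRV by the same amount, the between-arm difference is zero and the test has nothing to find, however large the shared improvement.

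The data needed for the within-person question are not secured either. If the device goes on at or near the first class, no baseline exists, and it cannot be recovered once classes have started.

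A between-arm HRV comparison without baseline adjustment would also reflect who is in each arm. Allocation is not described as random. Under section 12.5, for anyone unable to take part in yoga, "they will be assigned to meditation and the next two participants will be assigned to yoga".

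Section 13.1 says the pilot should supply estimates for the power analysis of a later grant application. Without a baseline window there is no HRV change to estimate.

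**Working it through.** The documents give no power or precision figure for HRV, and section 13.2 is blank, so there is no stated figure to reproduce.

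**1. Calendar**
- Wear: 6 × 7 = 42 days (section 12.3).
- Intervention: 6 × 7 = 42 days (section 12.5).
- Guaranteed days outside the intervention: 42 − 42 = 0.
- If wear starts L days before a full 42-day intervention and lasts 42 days, then L days are recorded before it and 42 − L days during it. The last L intervention days are lost: 1, 3 or 7 days for L = 1, 3 or 7.
- Covering a 7-day lead-in and the whole intervention needs 7 + 42 = 49 days.

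**2. What each analysis in section 13.1 can say about Aim 2(b)**

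| Planned item | Contrast | Tests pre-to-post HRV change? |
|---|---|---|
| HRV t-test | Meditation vs yoga; time point not stated | No |
| Non-parametric test of change | Meditation vs yoga | No; it also needs an HRV baseline |
| Within-arm Cohen's d | Before vs after | Describes only; needs an HRV baseline |

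**3. Size of the mismatch**

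Assumptions, none of them from the documents: both arms improve by 0.5 SD of the raw measure; pre-post correlation ρ is 0.5, 0.7 or 0.8; two-sided alpha 0.05; complete data. Total N is 30 (one cohort, 15 per arm) or 60 (both cohorts).

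The SD of change is √(2(1 − ρ)) raw SD, so the standardised change is 0.5 / √(2(1 − ρ)):
- ρ = 0.5: 0.5 / 1.000 = 0.50
- ρ = 0.7: 0.5 / 0.775 = 0.65
- ρ = 0.8: 0.5 / 0.632 = 0.79

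Rejection rates from 40,000 simulated trials per setting:

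| Test | N | ρ = 0.5 | ρ = 0.7 | ρ = 0.8 |
|---|---|---|---|---|
| Between-arm t, end values | 30 | 5.0% | 5.0% | 5.0% |
| Between-arm t, change | 30 | 5.0% | 4.9% | 5.1% |
| Pooled paired t | 30 | 75.9% | 92.6% | 98.7% |
| Between-arm t, end values | 60 | 4.9% | 5.1% | 5.1% |
| Between-arm t, change | 60 | 4.8% | 5.1% | 4.9% |
| Pooled paired t | 60 | 96.7% | 99.8% | 100.0% |

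An exact non-central t calculation at ρ = 0.5 gives 75.4% (N = 30) and 96.8% (N = 60), in agreement. In a separate run, a Mann-Whitney test on change scores, with both arms improving by 0.5 or 1.0 SD of change, rejected in 4.2% to 4.7% of trials. The general non-parametric test is therefore no better placed than the t-test.

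**4. Precision of a pooled change estimate**

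The 95% CI half-width in SDs of change is t(0.975, N − 1) / √N:
- N = 30: 2.045 / 5.477 = 0.373
- N = 60: 2.001 / 7.746 = 0.258

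In raw SD at N = 30 this is 0.373 × 1.000 = 0.37 for ρ = 0.5, 0.373 × 0.775 = 0.29 for ρ = 0.7, and 0.373 × 0.632 = 0.24 for ρ = 0.8.

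**The case against.** The strongest reply has three parts.

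**Wear may bracket the intervention.** Questionnaires are given only at the baseline and post-intervention visits, so section 8.3 is naturally read as hand-out at the one and return at the other. Sessions might also span fewer than 42 days: Monday of week 1 to Thursday of week 6 would be 39 days, leaving 3 of the 42. This stands as a plausible reading, and it makes the count of lost days illustrative. It does not set any minimum number of days before the first session, and it leaves the HRV windows undefined.

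**A pre-post summary is already planned.** If HRV counts as a continuous intervention outcome, the within-arm Cohen's d applies to it, and estimating rather than testing is acceptable in a pilot. It is true that an estimate with a confidence interval would serve here without a formal test. But the planned quantity is descriptive, no interval is attached to it, and it needs the missing baseline.

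**The lack of a within-arm test is not peculiar to HRV.** The psychosocial hypothesis 2(a) shares it. However, the belonging, mindfulness, anxiety and perceived-stress scales are listed at both visits, so their change can be computed. HRV has no such assured pair of measurements.

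It is also fair to say that the 5% figure follows by construction and that the paired-test figures depend on the assumed effect and correlations. They show the scale of the mismatch and do not predict this trial's result.

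**Conclusion.** The concern holds. Zero pre-intervention HRV days are guaranteed, neither a baseline nor an end window is defined, and every planned test that could apply to HRV compares the two active arms. Followed exactly, the plan would not test Aim 2(b) and could leave a baseline gap that cannot be repaired.

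The calendar and contrast arguments need no assumed effect size. Under the stated assumptions, a shared 0.5 SD improvement would be missed by the between-arm test in about 95% of trials. A pooled paired test would detect it in 76% to 99% with 30 participants and in about 97% or more with 60. Dropout and days without wear would lower those figures.

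This should be fixed before the first session. It affects a non-primary aim and the HRV inputs to the later power analysis; the feasibility and acceptability outcomes are untouched.

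**What to change.** **Section 12.3**
- State that wear starts at the baseline visit, a fixed number of days before the first session (about one week, for example; fewer could serve), and continues to the post-intervention visit.
- Define baseline HRV as the participant's mean of the 24-hour values over the lead-in days.
- Define end HRV as the mean over the same number of days ending at the post-intervention visit, and say whether those days overlap the last sessions.
- Use one mean per participant per window.

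**Section 13.1**
- Make the Aim 2(b) HRV analysis the pooled within-person change, end minus baseline, with a 95% CI.
- Adjust any yoga-versus-meditation HRV comparison for baseline HRV.
- State that, with no untreated control, the pre-post contrast shows change and not a causal effect.

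**Cost.** A few extra days of wearing a device the participant already holds (about a week in the example), plus wording in two sections. The downsides are slightly more wear burden and a fixed lead time before the first class in each cohort. The documents do not say whether devices are reused; if they are, the schedule for the second cohort must allow for it.

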For each yoga class, the instructor will lead the student through a series of yoga poses. Class will begin with centering and breathwork (pranayama) for 5-10 minutes. This will be followed by a series of warm-up poses (~5-10 minutes). After the warm-up sequence, students will flow through traditional sun salutations (~10-15 minutes). This will be followed by a series of standing poses (~ 15 minutes). Students will then be guided to flow through a series of cool-down poses on the floor (~10 minutes). Class will conclude with traditional Savasana during which affirmations or meditation are provided (~5-10 minutes).

Treatment fidelity:

Delivery: Standard treatment manuals and checklists have been developed. To ensure that the interventions are delivered as intended, yoga instructors will complete standardized checklists after each in-person session.³⁹ In addition, we will select one yoga session every 2 weeks for rating by trained research personnel. The PI and interventionists will meet to discuss results and problem solve. We will track participant's completion of study components using summary sheets for each visit. Participants will log attendance at intervention sessions using the mEMA app.

Post-intervention session: During the post-intervention assessment session, participants will be administered a structured questionnaire with a research team member via the secure REDCap system. Self-report questionnaires will be completed: 1) Sense of Belonging Scale (SBS); 2) Mindfulness Attention Awareness Scale (MASS) 15-item; 3) Generalized Anxiety Disorder-7 (GAD-7); 4) NIH toolbox measure of perceived stress. Participants will complete semi-structured (See Attachment G) interviews to help us collect data pertaining to the MBIs and delivery preferences. Interview responses will be transcribed in the REDCap system. These data will be used to adjust the content and format of the intervention based on feedback from participants who are our intended users.

13. Data Analysis

13.1. Describe the data analysis plan, including any statistical procedures.

Consistent with the scope of pilot projects, the proposed study will allow us to examine barriers to successful completion of the study, evaluation of acceptability of methods to participants, and estimates for future power analysis for a subsequent NIH R01 application. Numerical and graphical summaries will be computed for all measurements.

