Aim 1: To assess precision of estimates, 95% confidence intervals will be calculated for rates of recruitment into study, retention to end of study, and participants completing all training sessions. Overall adherence will also be described by calculating the mean and standard deviation of the number of completed training sessions per participant. Qualitative Analyses: Qualitative descriptive analysis⁴⁰ will be used to create a comprehensive summary of the acceptability of the MBI to participants. Deductive analysis will be used to determine common themes related to acceptability in the domains of affective attitude, burden, ethicality, intervention coherence, opportunity costs, perceived effectiveness, and self-efficacy.⁴¹ Interview responses will be reviewed by two members of the research team to identify themes. Themes and preliminary interpretations will be regularly presented to the larger research team to resolve any discrepancies or disagreements and check for alternative interpretations.

Aim 2: Participant characteristics and baseline survey responses will be described using means and standard deviations (SD) for continuous variables and number (percentage) for categorical variables. Continuous intervention outcomes will be described using means and standard deviations and, due to sample size, difference scores from baseline for intervention outcomes will be compared between groups using non-parametric statistical tests. Cohen's d, as a descriptive statistic, will be used as an effect size measure to quantify the extent of within group and between group differences in means over time.⁴² Long-term HRV (time domain and frequency domain measures derived for each 5 minute epoch within a 24 hour period will be averaged) measures will be compared between meditation and yoga groups by t-test. EMA and HRV data will be merged into a single dataset, matching upon timestamp.

Five-minute heart rate epochs immediately following completion of each mEMA survey will be selected for analysis.^{20,34}

13.2. Provide a power analysis, if applicable.

14. Provisions to Monitor the Data to Ensure the Safety of Subjects

This section is required when research involves more than Minimal Risk to subjects. Describe:

N/A – The PI believes this study constitutes no more than minimal risk for potential participants. Therefore, a Data and Safety Monitoring Plan is not required.

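### Class attendance, the basis of the primary adherence measure, rests on participants' own app entries, with no stated staff roster, reconciliation or rule for an unlogged class

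*Combined protocol and SAP*

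**What the plan says.** **Status of the measure.** Section 1.1 (Aim 1) defines feasibility to include class attendance: "Feasibility will be assessed as rates of recruitment, retention, and adherence to the MBI (% training sessions attended"). Section 7.1 makes feasibility primary: "Primary outcomes of interest of this study include the feasibility and acceptability of mindfulness-based interventions (MBI) (Aim 1").

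**Analysis.** Section 13.1 uses attendance in two ways. One is a completion rate: "95% confidence intervals will be calculated for rates of recruitment into study, retention to end of study, and participants completing all training sessions". The other is a count: "Overall adherence will also be described by calculating the mean and standard deviation of the number of completed training sessions per participant".

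**Source of the data.** Section 12.5, Intervention Delivery, says: "Attendance will be tracked via the Ilumivu platform. Participants will be requested to log attendance at each session via the app". The Treatment fidelity paragraph repeats it: "Participants will log attendance at intervention sessions using the mEMA app".

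**Other records named.** The same paragraph mentions two.
- Instructor checklists: "yoga instructors will complete standardized checklists after each in-person session". They are introduced as a check on delivery. None is described for meditation.
- Summary sheets: "We will track participant's completion of study components using summary sheets for each visit". The text does not say whether a class counts as a visit. The next sentence assigns attendance at classes to the app.

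No sign-in sheet, roster, reconciliation step or rule for an unlogged class appears in the protocol.

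**The concern.** The classes are held in person and led by study instructors, yet the stated attendance record is an entry that each participant is asked to make on a phone. The same app also carries three short surveys a day and daily reminders about the wearable (section 12.3). The programmed alert is described for the surveys. None is described for logging attendance.

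With this source alone, a blank has two possible meanings: the person was absent, or was present and did not log. An entry also has two: the person was present, or logged without attending. The adherence figure therefore combines attendance with logging behaviour, and the plan gives no means of separating them reliably.

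Section 13.1 says the pilot is meant to show barriers to completion and to inform a later grant application. If reluctance to use the app is read as reluctance to come to class, the wrong component may be redesigned. Attendance that was not recorded at the time cannot be reliably reconstructed later.

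**Working it through.** The plan states no expected adherence, logging rate or feasibility threshold, so there is no figure of its own to reproduce. The consequences below are conditional on assumptions.

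**Inputs from the protocol**
- Required classes per participant: 2 per week × 6 weeks = 12 (section 12.5).
- Classes offered per arm: 4 per week × 6 weeks = 24 (section 12.5).
- Participants per cohort: 30, with 15 per condition (sections 12.2 and 12.5).

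**Assumptions**
- Per-class logging rate *q* among attended classes: 99%, 98%, 95% or 90%.
- A blank is scored as an absence.
- Completing all sessions means 12.
- In steps 1 to 3, no class is logged falsely.
- In steps 1 and 2, logging is independent between classes.

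**Step 1. A participant who attends all 12 classes.** P(classed as complete) = *q*^12. Expected number logged = 12*q*.

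| Logging rate *q* | *q*^12 | Mean logged of 12 |
|---|---|---|
| 99% | 0.89 | 11.88 |
| 98% | 0.79 | 11.76 |
| 95% | 0.54 | 11.40 |
| 90% | 0.28 | 10.80 |

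The mean loses 1% to 10%. The completion rate loses 11% to 72% of the true completers.

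**Step 2. Effect on the reported interval.** Assume 80% of a cohort of 30 truly complete, that is 0.80 × 30 = 24. The expected recorded number is 24 × *q*^12, rounded. Intervals are Clopper-Pearson 95%.

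| Logging rate | Recorded | Rate | 95% CI |
|---|---|---|---|
| complete | 24/30 | 80% | 61% to 92% |
| 98% | 24 × 0.785 ≈ 19/30 | 63% | 44% to 80% |
| 95% | 24 × 0.540 ≈ 13/30 | 43% | 26% to 63% |
| 90% | 24 × 0.282 ≈ 7/30 | 23% | 10% to 42% |

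At 95% logging the interval lies wholly below the true 80%.

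**Step 3. If logging clusters by person.** Some people log nearly always and others seldom. With a beta-binomial model and an assumed intraclass correlation of 0.3, put *s* = (1 − 0.3)/0.3 = 2.333. Then P(all 12 logged) is the product over *i* = 0 to 11 of (*qs* + *i*)/(*s* + *i*). The results are 0.95, 0.91, 0.79 and 0.62 at 99%, 98%, 95% and 90% logging. The loss is smaller than under independence but does not vanish. The means do not change.

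**Step 4. Errors in both directions.** Let *a* be true attendance, *m* the share of attended classes not logged, and *f* the share of missed classes logged anyway. Recorded attendance = *a*(1 − *m*) + (1 − *a*)*f*.
- *a* = 0.75, *m* = 0.05, *f* = 0: 0.7125, a bias of −3.75 points.
- *a* = 0.75, *m* = 0.10, *f* = 0: 0.675, a bias of −7.5 points.
- *a* = 0.75, *m* = 0.05, *f* = 0.15: 0.7125 + 0.0375 = 0.75, no net bias.
- *a* = 0.60, *m* = 0.05, *f* = 0.15: 0.57 + 0.06 = 0.63, a bias of +3 points.

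The sign depends on the balance of the two errors, and the plan gives no information on either.

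**The case against.** **The stronger reading.** A reader might infer that every forgotten log will count as a missed class, so that adherence is certain to be biased downward. The documents do not support this. They state no scoring rule for a blank: it could be an absence, a query or a missing value. Unverified self-report can also err upward. Participants are required to attend twice a week, and the principal investigator leads yoga classes, so some pressure to log is conceivable. Step 4 shows that false logs can cancel or reverse the bias.

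**Other records may exist.** The summary sheets could cover classes, and the content of the instructor checklists is not in the text available. That stands as an ambiguity. It does not close the gap: the text assigns class attendance to the app twice, and checklists are described for yoga only. An anonymous head count would not verify the logs either, because section 29.1.1 lets colleagues take part in the program without joining the study.

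**App fatigue can partly be seen.** Surveys are timestamped, so someone who answers them but logs no class looks different from someone who has abandoned the app. This is fair, but it does not show whether a given class was attended. It should also not be assumed that the surveys run for six weeks. Section 12.3 gives that duration for wearing the device and none for the surveys.

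**The size is assumed.** The logging rates have no basis in the documents, independence exaggerates the loss (step 3), and section 13.1 does not say whether all sessions means 12 or 24. All of this stands, and the figures are therefore conditional.

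**Weight.** Adherence is one of three named components of feasibility. It is described without a progression threshold, so no decision rule is shown to change.

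**Conclusion.** The point holds as a gap in measurement. The stated source for a primary feasibility measure is an unverified participant entry, with no roster, reconciliation or missing-log rule. What is recorded is attendance mixed with logging behaviour.

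The direction and size of the error are not established. If blanks count as absences and omissions outweigh false logs, adherence is understated, and the all-sessions rate suffers far more than the mean. At an assumed 95% logging, a full attender is classed as complete with probability 0.54 under independence, or 0.79 with the clustering assumed in step 3. The mean is 11.4 of 12 in both cases. These figures rest on a denominator of 12 and on assumed logging rates.

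The change is worth making: it deals with omissions, false logs and the missing rule together, and it must be in place before the first class.

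**What to change.** 1. Make a sign-in by study ID, without names, the source record for attendance at every class in both arms. The instructor already in the room checks it against the people present.
2. Keep the app log as a secondary measure. Report its agreement with the sign-in as a feasibility result on app compliance.
3. State how discrepancies are resolved and how a class with no record in either source is scored.
4. State in section 13.1 whether all training sessions means the 12 required or the 24 offered.
5. Say whether the summary sheets cover classes.

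**Cost.** One sheet per class: 8 classes a week across the two arms, so 8 × 6 = 48 sheets per cohort. No extra staff should be needed.

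**Downside to manage.** Section 16.2 limits access to identifiers to the principal investigator or a designated coordinator, and section 29.1.1 means that colleagues outside the study may be in the room. The sign-in must not reveal who is enrolled. One way is for everyone present to hand in a folded slip, with a study ID on it only if they are enrolled. The instructor checks that slips match heads, and the coordinator transcribes the IDs.
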